6.4 Data Analysis

Drs. [name] and [name], our epidemiology and biostatistics experts will conduct all analysis. They will compare the distribution of patient characteristics between the unexposed observations from the control period and the exposed observations during the intervention period, which are analogous to distributions across arms in a parallel cluster randomized trial. Then, they will plot rates of our outcomes over each three- month time period, comparing how rates differ from the control period to the intervention period overall, within each clinic, and between urban and rural clinics to examine the effects of the intervention, time and level of urbanicity on the outcomes. To examine treatment effects for our primary and secondary outcomes related to receipt of all methods of contraception, we will use a generalized linear mixed model, adjusting for the confounding effect of time with the random effect for CHC site and fixed effect for each time interval.⁵³

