6.0 Aim 2 Research Design, Methods, and Data Analysis

Aim 2 is to implement linked PP contraception and newborn care in 7 CHCs and evaluate the effect on provision of PP contraception and rates of short-interval pregnancy. We hypothesize that a linked PP contraception care with newborn care model can be implemented successfully in urban and rural CHC settings. PP women offered contraceptive care linked with newborn care would be more likely to receive any form of contraception at two months PP and by six months PP. Additionally, we hypothesize that CHCs will have a lower rate of short IPIs among incoming prenatal patients after implementing the linked contraception care with newborn care model compared with their rate prior to implementation.

Using a novel approach, we will test a patient-oriented alternative delivery system for PP contraception that will fill a gap in our current system resulting in improved contraceptive access for women. We will use a cluster randomized cross-sectional stepped wedge design to test the novel linked contraception and WBV model's impact on increasing PP contraception uptake in urban and rural CHCs, compared to usual care. We will include the 7 CHCs (six urban, one rural) recruited through Aim 1 of this project.

During the intervention period, staff will capture women during the first WBV (typically 3-5 days after delivery) and offer to have the next visit co-scheduled for infant and contraception care. Current practice at all AllianceChicago CHCs is to ensure all newborn infants leave the clinic with the next visit already scheduled. Appointments are scheduled during the discharge process at the end of each visit. During the discharge process all women 0-6 months postpartum who are established patients will be identified by an electronic prompt in the infant's electronic medical record. The prompt will instruct staff to offer the mother a co-scheduled visit for newborn and contraceptive care at the time of the next newborn visit.

Those who agree will be co-scheduled and those who are not in need of care, or do not wish for co-scheduled care, can decline. Women will be excluded if they had a tubal ligation or a long acting reversible contraception planned immediately after delivery. Women will be offered this co-scheduling option at each WBV through six months PP. Repeat opportunities for co-scheduled care are important as women's needs and

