We will conduct a cluster randomized, cross-sectional stepped wedge study to roll out the intervention across sites and assess the change in clinical and implementation outcomes from before to after the adapted intervention is introduced into clinics. The cluster, or unit of analysis, is the clinic (not individual), which is critical for a system-level intervention. In a stepped wedge study, the design is extended so that every cluster provides before and after observations and every cluster switches from the control (usual care) to the intervention condition (linked care) at regular intervals ("steps"), at different points in time. The order in which a cluster switches from control to intervention is randomized. The advantages of the stepped wedge design are that it provides a pragmatic and robust approach to testing the effectiveness of health service delivery interventions (53). The stepped wedge design is pragmatic because the intervention can be rolled out over time. Additionally, no individual patient consent is required for this system-level health service delivery intervention, and therefore outcomes may be obtained through routinely collected de-identified data from the common AllianceChicago EHR. It is a robust design because each cluster provides data under both the control and intervention condition and therefore may serve as its own control, improving the precision of the study. A limitation of the stepped wedge design is the confounding effect of time given that clusters switch over to the intervention at different times. To help control for the effect of time, 4 additional clusters will be randomized to either the control or the intervention for the entire study period, as in a traditional parallel cluster randomized trial.

One urban and one rural CHC site will be randomized to each step occurring at 3-month intervals. Each step includes a 3-month transition period when the individual clinics will prepare to implement linked care. The design is cross-sectional because outcomes are obtained from the subset of patients seen during each time period at each clinic rather than following individually recruited patients over time.

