6.2 Outcome Variables

Primary outcome:

- **Receipt of all methods of contraception by two months PP.** Using de-identified patient-level EHRS data for eligible women at each clinic within each time interval, we will create a dichotomous variable for receiving any contraception by two months PP. We will work with AllianceChicago's IT team to restrict the data pull to eligible women who attended an infant 3-5 day WBV after the study period began.

Secondary outcome:

- **Receipt of all methods of contraception by six months PP.** This outcome will be calculated similar to the primary outcome with the exception of time-period.
- **Short IPI pregnancies.** During the baseline period (control condition) and 18 months after the introduction of the intervention in each CHC, we will use EHRS data to estimate the clinic-level rate of incoming prenatal patients presenting with a short IPI.

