6.5 Expected Outcomes

Intervention: After the intervention period begins, postpartum women within the selected CHC sites will be more likely to receive any contraceptive method by two and six months postpartum. We anticipate a minimum absolute increase in contraception use of 15% (from 45% to 60%) and a decrease in short IPI pregnancies from approximately 35% to 20% from before to after the intervention, both of which would have a clinically meaningful impact on the population.

Implementation Process: By the end of Aim 2, we expect the intervention will be implemented successfully at all sites. However, important clinic-level and system-level barriers will be identified at each site. For example, the discharge process likely occurs in slightly different ways in each clinic, which may impact who responds to the alert in the EHR and the efficiency in which the co-scheduling can be accomplished.

All modifications (i.e. custom fields, prompts) within EHR and scheduling software have been built. Participating CHC's have been randomized for the intervention. All sites entered the control period April 1, 2021 and the first site will enter the intervention period August 1, 2021.

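### The contraception model adjusts only for site and time, so clinic-specific changes in patient mix stay in the estimate; a short list of maternal covariates should be pre-specified

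*Combined protocol and SAP*

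**What the plan says.** Section 6.4 opens with a descriptive step: "They will compare the distribution of patient characteristics between the unexposed observations from the control period and the exposed observations during the intervention period". It does not list the characteristics and does not say what follows if they differ. After plots of rates, it specifies a generalised linear mixed model for the contraception outcomes, "adjusting for the confounding effect of time with the random effect for CHC site and fixed effect for each time interval". The link function is not given. No patient covariate, covariate-adjusted analysis or rule for acting on an imbalance appears there or elsewhere.

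Four features of the design bear on this:

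- **Clusters (section 6.0).** "We will include the 7 CHCs (six urban, one rural) recruited through Aim 1 of this project".
- **What is randomised (section 6.0).** "The order in which a cluster switches from control to intervention is randomized".
- **Sampling (section 6.0).** The design is cross-sectional: "outcomes are obtained from the subset of patients seen during each time period at each clinic rather than following individually recruited patients over time".
- **Data (section 6.2).** The primary outcome is built as follows: "Using de-identified patient-level EHRS data for eligible women at each clinic within each time interval". The extract will "restrict the data pull to eligible women who attended an infant 3-5 day WBV after the study period began".

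Section 6.5 anticipates a rise in contraception use of at least 15 points, from 45% to 60%.

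**The concern.** Each clinic contributes different women in each period, and only the order of seven clinics is randomised. The women are identified after that randomisation, by attendance at a newborn visit. The mix of women behind the control and intervention observations can therefore differ. The documents themselves link patient characteristics to care: section 2.0 reports lower postpartum visit rates among African-American women and in high-poverty communities, and less timely contraception among low-income women.

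If a clinic's mix changes when it switches, the stated model credits the consequence to linked care. The planned comparison of characteristics cannot settle the matter. A crude control-versus-intervention table mixes drift common to all clinics, which the interval effects remove, with clinic-specific change, which they do not.

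Timing matters too. Section 6.3 gives the investigators real-time access and monthly reports that feed the outcomes. Covariates chosen later could be chosen with the results in view.

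**Working it through.** The documents state no sample size, power, alpha, intracluster correlation (ICC) or clinic-period size, so there is no figure of the plan's to reproduce. The check asks which kinds of case-mix difference pass through the stated model.

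**From the documents.** Seven clinics; random site effect; fixed interval effects; planned effect 15 points (45% to 60%).

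**Assumed.** The linear analogue of the model; one clinic per step, 8 periods, no transition gap; 15, 30 or 60 women per clinic-period; ICC 0.01, 0.05 or 0.10; outcome variance 0.25; one binary characteristic worth γ = 15 points of contraception use. Section 6.0 also mentions four additional clusters, and one urban plus one rural site at each step. Neither fits seven clinics with one rural, so the layout here is a simplification. That conflict is a separate matter to reconcile.

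**Formula.** The generalised least squares treatment estimate is a weighted sum of clinic-period means, with weights w(k,t) for clinic k and period t. An omitted characteristic with prevalence p(k,t) contributes γ × Σ w(k,t) p(k,t). Two properties hold whatever the ICC or clinic size:

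- In each period the weights sum to zero over clinics, so any drift common to all clinics contributes exactly 0.
- The weights sum to 1 over intervention cells, so a shift δ that occurs in every clinic at its switch contributes exactly γδ.

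**Common drift.** Take prevalence rising 20 points over the study, or 20/7 = 2.86 points per period. Numbering periods from 0, the intervention cells average period 5 and the control cells period 2. The crude contrast is off by 3 × 2.86 × 0.15 = 1.3 points; the model is off by 0.0.

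**Results, in points of risk difference:**

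| Pattern in the characteristic | Crude contrast | Model with site and interval |
|---|---|---|
| Common drift of 20 points | 1.3 | 0.0 |
| Stable clinic differences, SD 15 points | SD 0.85 | SD 0.05 to 0.33 at ICC 0.05 or 0.10; 0.40 to 0.88 at ICC 0.01 |
| Independent clinic-by-period variation, SD 10 points | not computed | SD 0.56 to 0.70 |
| Clinic-specific linear trends, SD 10 points over the study | not computed | SD 0.21 to 0.34 |
| 10-point shift at each clinic's switch | 1.5 | 0.10 × 15 = 1.5 |

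The model standard error over the same settings was 2.8 to 5.6 points. The upper value for stable differences (0.88) comes from 15 women per clinic-period with ICC 0.01, where the random effect removes essentially nothing.

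**Chance error against bias.** Rows two to four are standard deviations around zero under randomised order. As a rough guide, adding 0.70 in quadrature to its matching standard error of 2.9 gives √(2.9² + 0.70²) = 2.98. Only the last row is a bias.

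**Precision from adjustment.** A binary characteristic at 50% prevalence with an outcome difference d explains 0.25d² of variance. For d of 10 to 20 points that is 0.0025 to 0.0100. Outcome variance at 45% is 0.45 × 0.55 = 0.2475, so the share explained is 1.0% to 4.0%, which shortens the standard error by about 0.5% to 2.0%.

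**The case against.** The strongest reply is that the model is already a legitimate one. The order of switching is randomised, so chance differences in mix cause no expected bias, and the site and interval terms deal with the two most obvious patterns. An analysis without covariates is not an error in itself. All of this stands.

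It can also be said that nothing explains why going live would change who attends a newborn's first visit. Under section 6.0 a woman enters at that visit and the offer comes at discharge, so entry precedes her exposure. This largely stands. One possible route is left open. Section 6.0 excludes women with long-acting contraception planned immediately after delivery, section 6.1.2 does not list that exclusion, and neither says how it would be identified in control periods, before the prompt exists. Those passages should be reconciled, but they do not demonstrate differential sampling.

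A reader might infer that any difference in the planned table carries straight into the effect estimate. It does not: common drift drops out and stable differences are generally reduced. A reader might also multiply an assumed 5- to 15-point shift by an assumed 10- to 20-point outcome difference, obtain 0.5 to 3 points, and report a bias of up to 3/15 = 20% of the planned effect. The product is the model's bias only if the whole shift is specific to the switch. None of the inputs comes from the documents, and the upper end combines the two largest assumptions.

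The number of clinics is a weaker defence. It limits clinic-level covariates, whereas patient-level terms are estimated across all women.

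**Conclusion.** The point holds in a limited form and is worth acting on. As written, the contraception model leaves in the estimate any clinic-specific change in case mix over time, any change in who is sampled after a switch, and a remainder of stable clinic differences that is larger when the ICC and clinics are small. With seven clinics these add chance error, at most 0.9 points (SD) for any single pattern under the assumptions above, against standard errors of 2.8 to 5.6. They add bias only if the change is linked to the switch; the illustration is 1.5 points against a planned 15, or 10%. The sizes scale with the assumed shift and covariate effect, and the documents establish neither.

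The documents do not support a claim that the planned estimate is biased, nor that adjustment would bring a large gain in precision. What is missing is a pre-specified adjusted analysis, which the patient-level data and the planned comparison of characteristics should make feasible.

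**What to change.** In section 6.4, before outcome data are reviewed:

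- **Name a short list of maternal characteristics** from the planned comparison that are fixed before the first well-baby visit and available in the EHR. Age, parity, insurance and race/ethnicity are candidates only. Section 6.4 names no characteristics, and section 6.3 describes pulls of diagnosis, procedure and billing codes, so availability and completeness must be confirmed.
- **Add them as patient-level fixed effects** to the contraception model, keeping the random site effect and the interval effects.
- **State a rule for missing covariate values**, so that the adjusted and unadjusted models use a known set of women.
- **Report the site-and-time-only model alongside.**
- **State the link function, and report a standardised risk difference from both models.** Under a logit link, adding covariates changes the conditional odds ratio even without confounding, so the two odds ratios are not directly comparable.
- **Record the date of the choice and what had been seen**, given the monthly reports in section 6.3.

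The cost is SAP wording, somewhat more analysis work and dependence on EHR completeness. The expected gain in precision is modest. The main benefits are protection against a switch-linked change in the measured characteristics and a covariate set that cannot be chosen from the results.

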3.0 Objectives/Aims

Aim 1: Develop a comprehensive implementation plan to link PP contraception and newborn care through co-scheduling in community health centers. We will work with AllianceChicago to assess community health center fit and readiness. Guided by the *Consolidated Framework for Implementation Research (CFIR)*, we will interview administrators, staff, providers, and patients from each site with the goal of identifying factors that may facilitate or impede the development of an implementation plan for linked care.

All study activities for Aim 1 have been completed.

Aim 2: Implement linked PP contraception and newborn care in seven geographically diverse community health centers (six urban and one rural) and evaluate the effect on provision of PP contraception and rates of short-interval pregnancy. We will roll out the intervention across sites with a stepped-wedge, cluster-randomized design and use AllianceChicago's common electronic health record to evaluate effectiveness by comparing pre- and post-intervention outcomes including clinic-level provision of all methods of contraception at two and six months PP and clinic-level rates of short inter-pregnancy intervals.

Hypothesis: we hypothesize that providing PP women contraception care linked with newborn care through co-scheduling these visits will increase the number of women offered contraception prior to two and six months PP and reduce the number of short interval pregnancies.

All participating CHC's have been randomized for the intervention. All sites entered the control period April 1, 2021 and the first site will enter the intervention period August 1, 2021.

Aim 3: Assess implementation of linked PP contraception and newborn care and report on key barriers and facilitators related to successful implementation of the intervention. A mixed methods approach will be utilized to assess and document the implementation process using the *RE-AIM (Reach, Effectiveness, Adoption, Implementation, and Maintenance)* and CFIR frameworks.

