7.4 Expected Outcomes

We expect to identify important barriers and facilitators as a continuum during the implementation process at the clinician-level, clinic-level and system-level. Understanding those factors could help not only to improve the intervention at the local CHCs, but also will could increase understanding of similar interventions in the CHC setting. Findings will also result in understanding factors that may differ between urban and rural settings. Determining how implementation in CHCs vary over levels of urbanicity will be a valuable contribution to the literature. The process and results of this aim will be disseminated to contribute to the implementation science literature.

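### With one rural clinic among seven, the planned urban-rural comparison can describe that clinic but cannot show an effect of urbanicity on outcomes or implementation

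*Combined protocol and SAP*

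**What the plan says.** The clinic counts agree wherever they are given. Aim 2 in section 3.0 names "seven geographically diverse community health centers (six urban and one rural"; section 5.0 gives the same split; section 6.0 says "We will include the 7 CHCs (six urban, one rural) recruited through Aim 1 of this project". Section 6.0 also fixes the level at which evidence accrues: "The cluster, or unit of analysis, is the clinic (not individual), which is critical for a system-level intervention".

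Two places look for more than this split can give. In section 6.4, outcome rates are to be plotted by three-month period and the change from control to intervention compared overall, within each clinic, and "between urban and rural clinics to examine the effects of the intervention, time and level of urbanicity on the outcomes". In section 7.4, on implementation, the plan expects insight into factors that differ between urban and rural settings and adds: "Determining how implementation in CHCs vary over levels of urbanicity will be a valuable contribution to the literature".

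The treatment-effect model in 6.4 has no urbanicity term. It is described as "adjusting for the confounding effect of time with the random effect for CHC site and fixed effect for each time interval".

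Two statements in section 6.0 do not fit the clinic counts: "One urban and one rural CHC site will be randomized to each step occurring at 3-month intervals", and "4 additional clusters will be randomized to either the control or the intervention for the entire study period". No urban-rural split is given for the four clusters.

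**The concern.** Urbanicity is a property of the clinic, so the number of rural observations that bear on it is the number of rural clinics, which is one. Whatever distinguishes that clinic (staff, case mix, clinical champion, discharge workflow, the date it crosses over) is carried by the same indicator as rurality. Section 6.5 itself expects the discharge process to differ from clinic to clinic in ways that may affect who responds to the alert.

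Nothing in the plan says that the rural side of the comparison is a single site. A reader of the results could therefore take ordinary clinic-to-clinic variation for a finding about rural care, in a trial that stresses its relevance to both urban and rural health centers.

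**Working it through.** The documents give no sample size, ICC, between-clinic variance or precision for this comparison, so there is no planned figure to reproduce. Three checks were made.

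**1. Can the effect be identified?** Take an illustrative stepped wedge with 7 clinics, 8 periods, one clinic crossing over per step, and one clinic labelled rural.

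| Model | Columns | Rank |
|---|---|---|
| Clinic + period + intervention | 15 | 15 |
| ... plus rural | 16 | 15 |
| ... plus rural × intervention, one common effect otherwise | 16 | 16 |
| Clinic + period + clinic-specific intervention effects | 21 | 21 |
| ... plus rural × intervention | 22 | 21 |

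Once clinic effects are in the model, the rural indicator adds no rank: it is that clinic's indicator. If the intervention effect may differ by clinic, rural × intervention adds none either. It becomes estimable only on the assumption that effects are equal across clinics apart from rurality. A random-intercept model could return a rural coefficient, but only by borrowing the urban clinics' variance, since variance among rural clinics cannot be estimated from one.

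**2. What could a label permutation show?** With 1 rural clinic of 7 there are 7 possible assignments of the label. The smallest one-sided p-value is 1/7 = 0.143, whatever the data.

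**3. How large is chance variation in the planned comparison?** Section 6.4 compares change from control to intervention, so the relevant quantity is the rural clinic's effect minus the mean effect of the six urban clinics.

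- Inputs: 1 rural and 6 urban clinics (sections 3.0, 5.0, 6.0); anticipated effect 60% − 45% = 15 points (section 6.5); SD of the true effect between clinics taken as 3, 5 or 8 points (assumed).
- Assume no urbanicity effect and ignore within-clinic sampling error.
- 95% range = ±1.96 × SD × √(1 + 1/6) = ±1.96 × 1.080 × SD = ±2.117 × SD.

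| Assumed SD of effect | 95% chance range |
|---|---|
| 3 points | ±6.4 points |
| 5 points | ±10.6 points |
| 8 points | ±16.9 points |

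The number of patients does not enter the formula. Within-clinic sampling error would widen these ranges. So would having to estimate the SD from the six urban clinics: with 5 degrees of freedom the multiplier rises from 2.117 to about 2.78, giving half-widths of about 8 points (2.78 × 3) to 22 points (2.78 × 8).

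**The case against.** The strongest reply is that the plan promises little here. For outcomes, the comparison is a set of plots. The model has no urbanicity term or interaction, no test is planned, and neither the aims nor the hypothesis in section 3.0 mention an urban-rural effect. The same sentence plots each clinic separately, so a careful reader would see that the rural group is one line. Most of this stands: the fault is one of interpretation, not of the main analysis. It does not remove the point, because the stated purpose of the plots is to examine an effect of urbanicity and section 7.4 goes further for implementation.

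Four stronger readings are tempting and are not supported.

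- A reader might infer that the primary treatment effect is biased. The urban-rural label plays no part in that model.
- A reader might size the problem by how far one clinic's rate sits from the average of six: about ±11, ±24 or ±33 points at a 45% rate and assumed ICCs of 0.01, 0.05 or 0.10. Those figures describe a difference in level. A stable clinic level cancels in the control-to-intervention change that 6.4 compares.
- A reader might conclude that every rural-urban contrast should be dropped, including qualitative ones. Case contrasts are legitimate in a mixed-methods aim, and informants may themselves attribute barriers to rural conditions.
- A reader might conclude that the main result applies only to urban clinics. The treatment effect is pooled over all seven, and an unreplicated subgroup contrast does not change that.

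It can also be said that section 6.0, with one rural site per step, implies more rural clinics. That cannot be met with one rural clinic, and every explicit count gives one. If reconciliation showed several rural clinics, this point would weaken.

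**Conclusion.** The point holds as a limit on what may be concluded. The design cannot distinguish rurality from the single rural clinic, so neither the inference sought in 6.4 nor the one expected in 7.4 is available. This lack of identification follows from the clinic counts and needs no assumed variance.

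The size does rest on an assumption. At the upper end of the assumed range for the between-clinic SD, chance alone could produce a rural-urban difference in effect as large as the whole anticipated benefit. At the lower end it could produce one of roughly two-fifths of it (6.4/15 = 0.43). No primary or secondary treatment-effect estimate changes.

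**What to change.** - **Section 6.4:** label the urban-rural plots as a description of one rural clinic against six urban clinics, and state that no effect of urbanicity will be inferred from them.
- **Section 7.4:** replace the sentence on how implementation varies with urbanicity by a description of implementation at the single rural site. Keep qualitative contrasts, but attribute them to that site.
- **Sensitivity analysis:** report the pooled treatment effect with and without the rural clinic. This shows how far the result depends on that clinic; it is not a test of urbanicity.
- **Section 6.0:** reconcile the statement of one urban and one rural site per step, and the four additional clusters, with six urban and one rural clinics. State the urban-rural status and allocation of every cluster.

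The cost is wording changes and one extra model run, with no new sites or data. The downside is that the sponsor gives up a stated urban-rural claim.

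### The primary mixed model leaves no room for clinic rates to vary between quarters beyond the shared time trend; if they do, its standard error is too small

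*Combined protocol and SAP*

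**What the plan says.** Section 6.4 of the combined protocol and SAP is the whole analysis plan for receipt of contraception. The model is a GLMM, "adjusting for the confounding effect of time with the random effect for CHC site and fixed effect for each time interval". The intervention term is not written out. No clinic-by-period effect, clinic-varying intervention effect, robust variance or permutation test is listed there or elsewhere. Alpha, sidedness, the test and its degrees of freedom are not stated.

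The outcome is a yes/no variable per woman, built "Using de-identified patient-level EHRS data for eligible women at each clinic within each time interval" (section 6.2). Section 6.0 nevertheless says "The cluster, or unit of analysis, is the clinic (not individual), which is critical for a system-level intervention". Section 6.4 also plans plots of three-monthly rates, "within each clinic, and between urban and rural clinics to examine the effects of the intervention, time and level of urbanicity on the outcomes". The clinic count is given as "We will include the 7 CHCs (six urban, one rural) recruited through Aim 1 of this project" (section 6.0).

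**The concern.** A single random intercept per clinic gives two women at the same clinic the same correlation whether they attend in the same quarter or several quarters apart. In a stepped wedge, much of the information on the intervention comes from comparing quarters within a clinic, after removing the shared time trend. The noise in that comparison is sampling error plus any local quarter-to-quarter movement, such as staff turnover or supply. A binary outcome has no free residual variance to absorb the second part, so the model sets it to zero.

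The plan already assembles and plots the data by clinic and quarter, so the team will see such movement if it exists. The model would not carry it into the standard error. At stake are the width of the primary confidence interval and the level of the primary test. The point estimate is not at stake.

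**Working it through.** The plan states no power, sample size or error rate, so there is no figure of its own to reproduce.

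**Inputs from the documents.** 7 clinics (sections 3.0, 6.0, 6.1); baseline 45% and target 60% (section 6.5); 3-month steps (section 6.0).

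**Assumed inputs.** One clinic per step, which gives 7 + 1 = 8 quarters; ICC 0.01-0.05; CAC 0.8-1.0, where CAC is the share of the clinic-level variance that persists across quarters; m = 30, 60 or 100 women per clinic-quarter; two-sided 5% Wald z test.

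**Worked cell: ICC 0.05, CAC 0.8, m = 60** (linear approximation on clinic-quarter rates)

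- v = p(1 − p) = 0.45 × 0.55 = 0.2475
- Sampling variance of a clinic-quarter rate: v(1 − ICC)/m = 0.2475 × 0.95/60 = 0.00392
- Persistent clinic variance: v × ICC × CAC = 0.2475 × 0.05 × 0.8 = 0.00990
- Clinic-by-quarter variance: v × ICC × (1 − CAC) = 0.2475 × 0.05 × 0.2 = 0.00248

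The stated model uses the first two variances (covariance V_m). The data have all three (V_t = V_m + 0.00248 I). With design matrices Z_i holding the quarter indicators and the intervention indicator:

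- Reported variance: A⁻¹, where A = Σ Z_i′V_m⁻¹Z_i
- Actual variance: A⁻¹(Σ Z_i′V_m⁻¹V_tV_m⁻¹Z_i)A⁻¹

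The reported SE is 0.0290 and the actual SE is 0.0368, a ratio of 1.269. As a rough check, √[(0.00392 + 0.00248)/0.00392] = 1.28. Type I error = 2Φ(−1.96/1.269) = 2Φ(−1.545) = 12.2%.

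**Grid, type I error (%) with the z test**

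| CAC | ICC | m = 30 | m = 60 | m = 100 |
|---|---|---|---|---|
| 1.0 | any | 5.0 | 5.0 | 5.0 |
| 0.9 | 0.01 | 5.3 | 5.6 | 6.1 |
| 0.9 | 0.02 | 5.6 | 6.3 | 7.3 |
| 0.9 | 0.05 | 6.7 | 8.6 | 11.1 |
| 0.8 | 0.01 | 5.6 | 6.2 | 7.2 |
| 0.8 | 0.02 | 6.2 | 7.7 | 9.6 |
| 0.8 | 0.05 | 8.5 | 12.2 | 16.9 |

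Six of the 18 cells with CAC below 1 exceed 8%; five of the six are at ICC 0.05. At 15 women per clinic-quarter the same formula gives about 5-7% throughout.

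**Simulation of the logistic GLMM** (2,000 runs per cell, Monte Carlo SE 0.5-0.8 points). At CAC 1 and m = 60: 5.3% (ICC 0.05) and 4.9% (ICC 0.02). At ICC 0.05 and m = 30/60/100: 7.3/10.1/11.6% (CAC 0.9) and 9.3/12.9/17.0% (CAC 0.8). The mean estimated effect under the null was −0.09 to +0.06 points, so there is no average bias.

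**Layout.** Section 6.0 says "Each step includes a 3-month transition period when the individual clinics will prepare to implement linked care"; dropping that quarter leaves the range unchanged. Steps of 2/2/2/1 agree to within 0.1 point. With 11 clusters, ICC 0.05 and CAC 0.8 the figures are 8.3/12.0/16.6%.

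**Reference distribution.** In the worked cell the stated model rejects 12.2% with z and 4.3% with t on 5 df (2Φ(−2.571/1.269)). At CAC 1 it rejects 5.0% and about 1.0%.

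**The case against.** The strongest reply is that nothing in the documents shows clinic rates varying in this way, and every input that sets the size is assumed. That stands. The high figures come from the top of the assumed ICC range or the largest clinics, and with small clinics the shortfall is minor.

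Second, section 6.4 is a one-sentence description that cites a stepped-wedge methods paper. The single common intervention effect is inferred from the absence of any other term. Because section 6.0 calls the clinic the unit of analysis, one could read the plan as a model for clinic-quarter rates with a free residual, which would absorb the variation. The patient-level variable in section 6.2 and the choice of a GLMM make that the less likely reading, but the plan should settle it.

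Third, a reader might infer that seven clinics are too few for the test to be valid. The calculations do not support this: when the stated variance structure is true, z holds about 5%. The missing alpha and degrees of freedom are a gap in prespecification, not evidence of inflation.

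Fourth, section 6.5 expects discharge routines to differ somewhat between clinics. That makes varying effects plausible, but it is said about implementation and gives no evidence on outcomes.

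**Conclusion.** The point holds as a conditional one. The stated model excludes clinic-by-quarter variation; if that variation exists, the standard error and interval are too small while the estimate is unbiased on average. Under the assumed grid, type I error runs from 5.0% (none) through about 5-7% (small clinics or low ICC) and about 9-12% (ICC 0.05, 60 women per clinic-quarter, CAC 0.9-0.8) to 17% at the extreme. The 17% should not be read as this trial's error rate, because the documents give none of the inputs it needs. The conclusion does not depend on whether there are 7 or 11 clusters. A better-protected analysis is available at modest cost, so the change is worth making before outcomes are analysed.

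**What to change.** 1. Add a random clinic-by-period effect to the primary GLMM, and say that the model is fitted to patient-level data.
2. Prespecify a permutation test over the allocations possible under the randomisation actually used, as the check on the primary p-value, and say which result governs if they disagree. This check matters because the clinic-by-period model alone can still run at about 6-8%: with t on 41 df it gave 5.8/6.2/7.5% at ICC 0.05 and CAC 0.8 (m = 30/60/100), and 8.1% when correlation decayed by a factor of 0.9 per quarter (ICC 0.05, m = 60). The simulated permutation test held 4.1-5.1%. Unrestricted, there are 7! = 5,040 orders with one clinic per step, or 7!/(2! × 2! × 2! × 1!) = 630 with steps of 2/2/2/1.
3. State the two-sided alpha and reference distribution in the same edit. One workable choice is t on clinic-period cells minus parameters: 56 − 7 − 7 − 1 = 41 in the 7 × 8 layout, or 35 − 7 − 4 − 1 = 23 with steps of 2/2/2/1.
4. Fit a clinic-varying intervention effect as a sensitivity analysis, since the clinic-by-period term does not cover it. With no drift but clinic effects varying with SD 2.5 or 5 points, the stated model's nominal 95% interval covers the average effect 93-94% or 86-92% of the time.
5. Reconcile, as a separate point, two statements in section 6.0 with the seven clinics: "One urban and one rural CHC site will be randomized to each step occurring at 3-month intervals" and "4 additional clusters will be randomized to either the control or the intervention for the entire study period". There is only one rural clinic, and 7 + 4 = 11. The permutation set and degrees of freedom depend on the answer.

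**Cost.** SAP wording and some programming, with no new data. Intervals widen by 1-42% over the grid at CAC 0.8-0.9. Nominal power for 45% to 60% at ICC 0.05 and CAC 0.8 falls from 92.8% to 89.0% (30 women per cell) and from 99.6% to 98.1% (60) with one clinic per step. With steps of 2/2/2/1 it falls from 76.7% to 65.2% and from 93.5% to 84.2%, about 9-12 points. Part of the power given up came from inflated type I error.
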